5.1 Atopic dermatitis

Atopic dermatitis (AD) is a chronic inflammatory skin disease that may affect up to 20% of children and up to 10% of adults. In its severe form, AD is characterised by widespread skin lesions, intractable itch, as well as increased susceptibility to bacterial, viral, and fungal skin infections (1-4). AD is associated with a substantial patient burden that typically includes poor quality of life and sleep disturbance (5).

AD is characterised by an activated T-helper-2 (Th2) pathway with increased expression of key Th2 cytokines including interleukin (IL)-13 (6,7). The expression of IL-13 is increased in lesional skin compared to non-lesional skin, and the proportion of CD4+ and CD8+ cells expressing IL-13 is upregulated in AD patients compared to individuals without AD (6, 8).

IL-13 acts on keratinocytes to release C-C motif chemokine ligand 22 and recruit more IL-13 expressing Th2 cells, decrease differentiation, and contribute to decreased barrier function (9). IL-13 also drives immunoglobulin E (IgE) production and contributes to mast cell activation status and, once allergen cross-links IgE on the cell surface, drives histamine release and induces itch (10, 11). Indeed, itch is a key issue in AD, which drives significant mechanical damage to the skin and further facilitates allergen and pathogen entry.

These effects together drive and exacerbate the disease phenotype. A review of the available preclinical literature from mouse and human ex vivo models suggests IL-13 as a, if not the, central mediator of the AD skin phenotype. Indeed, there is evidence that blocking the IL-4 receptor (which is part of the receptor complex that also binds IL-13) with the monoclonal antibody dupilumab leads to clinical improvement in subjects with AD (12).

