	Screening		Treatment														Details (protocol sections)
	1 ¹	2	3	4	5	6	7	8	9	10	11	12	13	14	15	16	
	-6	-2	0	2	4	6	8	10	12	14	16	18	20	22	24	26	
Visit	±3	-3	NA	±3	±3	±3	±3	±3	±3	±3	±3	±3	±3	±3	±3	±3	±3
Week																	
Visit window (days) ²																	
Trial population and eligibility																	
Informed consent ³	X																
Subject eligibility	X		X														Appendix 3B 8.1 to 8.3
Trial products and randomisation																	
Initiation of emollients (background treatment) ⁴		X															9.4
Concomitant medication (including rescue treatment)/ concurrent procedures	X		X	X	X	X	X	X	X	X	X	X	X	X	X	X	9.6
Randomisation			X														9.3
IMP administration, compliance			X ⁵	X ⁵	X	X	X	X	X	X	X	X	X	X	X	X	9.2
TCS (AxMP) dispensing			X	X	X	X	X	X	X	X	X	X	X	X	X	X	9.2.2
TCS (AxMP) return				X	X	X	X	X	X	X	X	X	X	X	X	X	9.8.3, 9.8.4
Investigator assessments at baseline																	
C-SSRS	X																11.2.5
Demographics (age), BSA involvement	X		X														11.2.1, 11.2.4
Other demographics and medical history	X																11.2.1, 11.2.2
Height, weight			X														11.2.3
Investigator assessment of efficacy																	
IGA	X		X	X	X	X	X	X	X	X	X	X	X	X	X	X	11.3.1
EASI	X		X	X	X	X	X	X	X	X	X	X	X	X	X	X	11.3.2
SCORAD	X		X	X	X	X	X	X	X	X	X	X	X	X	X	X	11.3.3

Panel 2 Schedule of trial procedures: screening and treatment period (continued)

	Screening		Treatment																Details (protocol sections)
	1 ¹	2	3	4	5	6	7	8	9	10	11	12	13	14	15	16			
	-6	-2	0	2	4	6	8	10	12	14	16	18	20	22	24	26			
Visit window (days) ²	±3	-3	NA	±3	±3	±3	±3	±3	±3	±3	±3	±3	±3	±3	±3	±3	±3		
Subject assessment of efficacy																			
eDiary training		X																	
eDiary ⁶																	11.3.4.1 to 11.3.4.3		
SF-36			X				X				X						11.3.4.4		
POEM			X	X	X	X	X				X						11.3.4.5		
DLQI			X	X	X	X	X				X						11.3.4.6		
EQ-5D-5L			X				X				X						11.3.4.7		
HADS			X				X				X						11.3.4.8		
Safety assessments																			
Vital signs	X		X	X	X	X	X	X	X	X	X	X	X	X	X	X	X	11.4.1	
Physical examination	X		X				X				X						11.4.2		
ECG	X		X				X				X						11.4.3		
Serum pregnancy test, hepatitis B, C, HIV	X																11.4.4		
Urine pregnancy test			X	X	X	X	X				X				X	X	11.4.4		
Serum chemistry, haematology, IgE	X ⁷		X	X	X	X	X				X				X	X	11.4.4		
Urinalysis	X		X				X				X				X	X	11.4.4		
Anti-drug antibodies			X								X						11.4.5		
Adverse events	X	X	X	X	X	X	X	X	X	X	X	X	X	X	X	X	13		
Other assessments																			

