Pharmacokinetics					X						X						X	11.5	
Photography ⁸			X		X						X						X	11.6.1	

- 1) For subjects who do not require a washout and subjects who only require washout of topical AD treatment (as specified in the exclusion criteria in Section 8.3), visits 1 and 2 will be combined and screening will be reduced to 2 weeks. Hence, these subjects will only attend visit 2 (Week -2) which will include all assessments shown under Week -6. The screening period has a planned maximum duration of 6 weeks.
- 2) If the date of a subject visit does not conform to the trial plan, subsequent visits should be planned to maintain the visit schedule relative to randomisation/baseline.
- 3) The informed consent form must be signed prior to performing any protocol-related procedures, including but not limited to screening evaluations and washout of disallowed medications. Additional informed consent is required for the photography component for the trial sites in scope.
- 4) All subjects must use an emollient twice daily (or more, as needed) for at least 14 days before randomisation and must continue this treatment throughout the trial (including safety follow-up).
- 5) For the first 3 IMP dosing visits (visits 3 to 5), subjects will be monitored after IMP administration for immediate drug reactions for a minimum of 30 minutes with vital signs taken every 30 minutes or until stable, whichever is later (see Section 9.2.1).
- 6) eDiary includes: Eczema-related Sleep NRS, Worst Daily Pruritus NRS, Patient Days of Topical Treatment Use; subjects will complete daily from Week -2 to 26, except for Patient Days of Topical Treatment Use which will be completed daily from Week 0 to 26.
- 7) IgE not assessed at screening.
- 8) Optional, selected trial sites only.

Abbreviations: AxMP, auxiliary medicinal product; BSA, body surface area; C-SSRS, Columbia-Suicide Severity Rating Scale; DLQI, Dermatology Life Quality Index; EASI, Eczema Area and Severity Index; ECG, electrocardiogram; eDiary, electronic diary; EQ-5D-5L, EuroQoL 5-Dimension Health Questionnaire 5 Level; HADS, Hospital Anxiety and Depression Scale; HIV, human immunodeficiency virus; IGA, Investigator's Global Assessment; IgE, immunoglobulin E; IMP, investigational medicinal product; NRS, numeric rating scale; POEM, Patient-Oriented Eczema Measure; SCORAD, Scoring Atopic Dermatitis; SF-36, 36-Item Short Form Health Survey; TCS, topical corticosteroid.

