5.2 Experience with investigational medicinal product

Tralokinumab is a human recombinant monoclonal antibody of the IgG4 subclass that specifically binds to human IL-13 and blocks interaction with the IL-13 receptors (13–15). A compilation of clinical and nonclinical data on tralokinumab including pharmacokinetics (PK) is given in the current version of the Investigator's Brochure.

In total, more than 4,340 subjects have been treated with tralokinumab (cut-off date: 18-Oct-2018) as determined from actual exposure data from completed clinical trials and the enrolment/randomisation schemes for ongoing trials. A phase 3 development programme is ongoing in AD, and other clinical trials with tralokinumab have been conducted in subjects with asthma, ulcerative colitis, idiopathic pulmonary fibrosis, and in healthy subjects. All

doses studied so far have had an acceptable benefit/risk profile and no major safety concerns have been identified. Possible risks associated with use of tralokinumab are summarised in Section 5.6.

In a phase 2b trial (D2213C00001), adults with moderate-to-severe AD on a background of mild to moderate topical corticosteroids (TCS) were treated with 3 different regimens of tralokinumab (45 mg every other week [Q2W], 150 mg Q2W, or 300 mg Q2W) or placebo to evaluate the safety and efficacy over a treatment period of 12 weeks. The primary endpoints were change from baseline in Eczema Area and Severity Index (EASI) at Week 12 and the percentage of subjects achieving Investigator's Global Assessment (IGA) response of 0 (clear) or 1 (almost clear) at Week 12. Secondary endpoints included change from baseline in EASI and Scoring Atopic Dermatitis (SCORAD) scores, and the percentage of subjects achieving at least 50% reduction from baseline in EASI and SCORAD scores (EASI50 and SCORAD50). In the overall intent-to-treat phase 2b population, an improvement in EASI score at Week 12 was seen in the tralokinumab 300 mg Q2W group versus placebo. 26% of subjects achieved an IGA of 0 or 1 in the tralokinumab 300 mg Q2W group versus 12% in the placebo group. The most commonly reported causally related treatment-emergent adverse event (AE) was upper respiratory tract infection (6 subjects [3.9%] in the combined tralokinumab group [45 mg, 150 mg, and 300 mg] and 2 subjects [3.9%] in the placebo group).

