9.3.1 Blinding

This is a double-blinded trial in which tralokinumab and placebo are visually distinct from each other. Neither the subject, nor the investigator or LEO staff who are involved in the treatment or clinical evaluation and monitoring of the subjects will be aware of the treatment received.

The packaging and labelling of the IMPs will contain no trace of identity. IMP is packed in identical boxes, with non-sequential kit numbers to ensure that unblinding does not occur during shipment and handling of the drug.

Since tralokinumab and placebo are visually distinct and not matched for viscosity, IMP will be handled and administered by a qualified, unblinded HCP (trained site staff) at the site who

will not be involved in the management of trial subjects and who will not perform any of the assessments.

If treatment allocation for a subject becomes known to the investigator or other trial staff involved in the management of trial subjects, LEO must be notified immediately.

Should an issue arise with the IMP (e.g., damaged kit or syringe that has been assigned to a subject prior to administration, or any other unexpected event with the kit or syringe [e.g., a malfunction during IMP administration]), the unblinded HCP at the site will contact the clinical research associate (CRA) to determine whether any specific actions are required. See Section 9.10 for details on reporting of product complaints.

The trial site will maintain a written plan detailing which staff members are blinded/unblinded and the process of IMP administration used to maintain the blind.

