11.4.4 Laboratory testing

11.4.4.1 Overview

Blood and urine samples will be collected according to the schedule of trial procedures (Section 4).

The evaluations shown in Panel 10 will be performed.

Panel 10: Clinical laboratory tests

Chemistry	Haematology
Alanine aminotransferase	Basophils
Albumin	Basophils/leucocytes
Alkaline phosphatase	Eosinophils
Aspartate aminotransferase	Eosinophils/leucocytes
Bilirubin ¹	Erythrocyte mean corpuscular haemoglobin concentration
Calcium	Erythrocyte mean corpuscular volume
Cholesterol	Erythrocytes
Creatinine	Haematocrit
Gamma glutamyl transferase	Haemoglobin
Glucose (non-fasting)	Leucocytes
HDL cholesterol	Lymphocytes
Lactate dehydrogenase	Lymphocytes/leucocytes
LDL cholesterol	Monocytes
Potassium	Monocytes/leucocytes
Protein	Neutrophils
Sodium	Neutrophils/leucocytes
Triglycerides	Thrombocytes
Tryptase ²	
Urea nitrogen	
Urinalysis	Serology
Glucose	Hepatitis B virus surface antigen ³
Ketones	Hepatitis B virus surface antibody ³
Leukocytes	Hepatitis B virus core antibody ³
Nitrite	Hepatitis C virus antibody ³
Occult blood	HIV-1 antibody ³
Protein	HIV-2 antibody ³
Pregnancy test ⁵	Immunoglobulin E ⁴
Choriogonadotropin beta	

- 1) If bilirubin is above upper limit of normal, direct and indirect bilirubin will also be measured.
- 2) Only measured in case of suspected anaphylaxis.
- 3) Measured at screening only.
- 4) Not measured at screening.
- 5) Only female subjects of child-bearing potential. Measured in serum at screening only, and in urine every 4 weeks thereafter (see Section 4).

Abbreviations: HDL, high density lipoprotein; HIV, human immunodeficiency virus; LDL, low density lipoprotein.

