11.4.4.2 Investigator evaluation of laboratory samples

Central laboratory

Chemistry, haematology, urinalysis (if applicable), serology, and serum pregnancy tests will be analysed by a central laboratory which will provide results to the trial sites. The investigator must evaluate all results outside the reference range ('clinically significant' or 'not clinically significant') and sign and date the evaluation. The signed and dated version will be filed with the investigator's trial documentation. Clinically significant abnormal tests (at randomisation and onwards) must be repeated to confirm the abnormality.

At each visit, the site staff will record in the eCRF if a sample was taken and, if applicable, the date and time as well as the investigator's assessment of the results ('normal', 'abnormal, not clinically significant', 'abnormal, clinically significant'). In addition, the subject's age (in years) must be provided in the eCRF at each visit where chemistry, haematology, and, serology is sampled.

If a screening laboratory result is abnormal and of clinical significance, it will be at the investigator's discretion to decide if the subject should be randomised into the trial (respecting exclusion criteria no. [26](#), [27](#), and [28](#)).

A serum pregnancy test must be taken at the screening visit in female subjects of child-bearing potential to rule out pregnancy prior to subject randomisation.

A laboratory manual will be provided to the trial sites specifying the procedures for collection, processing, storage, and shipment of samples, as well as laboratory contact information specific to this trial.

Tests performed at the trial site

Urine samples will be tested at the trial site with a dipstick; if abnormal, a urine sample will be sent to the central laboratory for further analysis.

At each visit, the site staff will record in the eCRF if a urine sample was taken and, if applicable, the investigator's assessment of the result ('normal', 'abnormal').

Female subjects of child-bearing potential will have a urine pregnancy test performed at the trial site at baseline prior to randomisation. The test will be repeated every 4 weeks as shown in the schedule of trial procedures in Section 4. The date and the outcome of the urine pregnancy test will be recorded in the eCRF ('positive', 'negative').

Reporting in eCRF

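### Post-baseline serum IgE, which the protocol links to the blocked cytokine, goes unmasked to the blinded investigator who scores efficacy: a potential and avoidable route to unblinding

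*Protocol*

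**What the plan says.** - **Mechanism.** Protocol Section 5.1: "IL-13 also drives immunoglobulin E (IgE) production and contributes to mast cell activation status". Section 5.2 says tralokinumab "specifically binds to human IL-13 and blocks interaction with the IL-13 receptors".
- **Sampling.** Panel 2 has a row "Serum chemistry, haematology, IgE" marked at baseline and at several treatment visits, with the footnote "IgE not assessed at screening". Panel 3 repeats the row at safety follow-up and early termination, and allows it at unscheduled visits.
- **Class of test.** Panel 10 puts "Immunoglobulin E" in the serology column. The hepatitis and HIV tests in that column are done at screening only.
- **Reporting.** Section 11.4.4.2: "Chemistry, haematology, urinalysis (if applicable), serology, and serum pregnancy tests will be analysed by a central laboratory which will provide results to the trial sites". Any value outside the reference range then has to be evaluated, signed and dated by the investigator, and the assessment goes into the eCRF.
- **Who is blinded.** Section 9.3.1: "Neither the subject, nor the investigator or LEO staff who are involved in the treatment or clinical evaluation" and monitoring is to know the treatment received.
- **Who scores.** Section 11.1 prefers one investigator to make all IGA, EASI and SCORAD evaluations for a subject. The only separation it requires is from IMP administration.
- **Planned use.** Protocol Section 14.3.13.3 plans summaries of change, a shift table and listings of laboratory parameters. SAP Section 6.7.4 adds nothing specific to IgE, and SAP Table 3 has no IgE limit.

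**The concern.** On the protocol's own rationale, blocking IL-13 could lower IgE. A series of IgE values could then hint at treatment allocation, and the stated reporting rule puts that series in front of the person who rates the disease.

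The primary endpoint, EASI75 at Week 16, is derived from investigator scoring. So are five of the nine secondary efficacy endpoints: IGA 0/1 at Weeks 16 and 26, change in SCORAD at Weeks 16 and 26 (which has a patient-scored component), and EASI75 at Week 26. Protocol Section 12 defends the design on the ground that the double blind limits observer bias. An unmasked marker related to the drug's target weakens that defence.

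**Working it through.** The plan gives no figure for IgE, so the main check is to follow one result through the documents.

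1. **Does IgE fall under the reporting rule?** Yes. IgE is serology in Panel 10, and Section 11.4.4.2 names serology without exception. The other serology tests are screening-only and IgE is not done at screening, so scheduled serology from baseline onward is IgE alone.
2. **Will out-of-range values arise?** The documents give no reference range. Raised serum IgE is a minor diagnostic feature of atopic dermatitis in Appendix 4, so such values are foreseeable.
3. **Does the recipient rate efficacy?** Both tasks are assigned to the investigator. No section assigns them to different people.
4. **Is there a mask elsewhere?** Section 9.3.1 covers packaging and kit numbers, handling and injection by an unblinded health care professional, a written plan of blinded and unblinded staff, and notification of the sponsor if allocation becomes known. None of these concerns laboratory results. The SAP has no mask either.
5. **Which results could matter?** Section 11.1 puts efficacy scoring before laboratory sampling, so the Week 16 sample cannot affect the Week 16 score. Only earlier samples can. The Panel 2 columns do not align reliably in the text available, so the exact weeks must be read from the published table. As they appear, several marks fall between baseline and Week 16. Laboratory turnaround is not stated.
6. **Does any rule need the site to see IgE?** It is not an endpoint (Panel 4), an eligibility test (Sections 8.2 and 8.3), a discontinuation criterion (10.2.1), an event of special interest (Panel 11) or an SAP Table 3 parameter.

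**Why no size is given.** Section 14.1 assumes 40% versus 15% EASI75 with 250 subjects, or 125 per arm. Its power figure reproduces and is not in dispute. The standard error is 0.0565 under the null (pooled rate 0.275) and 0.0542 under the alternative. Then (0.25 − 1.96 × 0.0565)/0.0542 ≈ 2.57, giving 99.5% against the stated 99%.

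Suppose raters guess the arm with accuracy *a* in both arms. Suppose also that a guess moves a fraction *x* of ratings, with non-responders moved up if active is guessed and responders moved down if placebo is guessed.

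- Shift on tralokinumab: *x*[0.60*a* − 0.40(1 − *a*)] = *x*(*a* − 0.40)
- Shift on placebo: *x*[0.85(1 − *a*) − 0.15*a*] = *x*(0.85 − *a*)
- Bias in the risk difference: *x*(2*a* − 1.25)

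| *a* | Bias |
|---|---|
| 0.50 | −0.25*x* |
| 0.625 | 0 |
| 0.75 | +0.25*x* |
| 1.00 | +0.75*x* |

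Neither *a* nor *x* is in the documents, and even the sign depends on *a*.

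**What a bias would cost if there were one (assumed values).** With no true effect, 15% response in both arms and 125 per arm, raising the active-arm rate by 1, 2 or 3 points lifts the chance of a false favourable result from 2.5% to 4.1%, 6.3% or 9.3%. This shows why the blind is worth protecting. It does not show that such a bias exists.

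**The case against.** The strongest reply has five parts.

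- **The fall is inferred.** Section 5.1 does not say that IL-13 is the only driver of IgE, or that IgE falls on tralokinumab by any amount within 16 weeks. The phase 2b account in Sections 5.2 and 5.4 reports no IgE result. This stands, and it limits the point to a potential route.
- **Scoring is structured.** Sections 11.3.1 and 11.3.2 require scoring of current disease, without reference to an earlier visit. EASI is built from four signs and an area score in four regions. This narrows the room for bias without removing it.
- **Section 9.3.1 does more than hide the syringe.** A reader might infer that it guards only against appearance and viscosity. That is too strong, since staff roles and notification are also covered. None of it reaches laboratory values.
- **IgE has a purpose.** A reader might infer that measuring it is pointless. The documents do not support that: it sits under safety assessments and will be summarised. What lacks a stated need is showing the values to the efficacy rater during the trial.
- **Timing and missing documents.** The SAP, dated October 2020, already refers to analysis of blinded data, so masking may come too late for released results. The laboratory manual was not available and may already mask IgE. Both affect the remedy. Neither supplies a safeguard in the protocol text.

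**Conclusion.** The gap is real and is a cheap improvement to the blind. Following Section 11.4.4.2 as written puts a target-related marker in front of the blinded efficacy rater, and nothing in the protocol or SAP prevents it.

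Two stronger readings should be resisted. A reader might infer that the trial was unblinded; nothing in the documents shows that. A reader might also attach a size, for example 1.5 to 3.8 points of bias from 0.75*x* at *x* = 2% to 5%. That needs every guess to be right (*a* = 1) and an invented *x*. Figures for how well IgE separates the arms would likewise need an assumed fall and an assumed variability. The size cannot be derived from the documents, and no estimate is offered.

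The conclusion assumes that the investigator who reviews the laboratory reports also rates efficacy, which the protocol allows but does not require. It also assumes that results from earlier visits arrive before the scored visit, and that the laboratory manual does not already mask IgE.

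**What to change.** - **Preferred.** State in Protocol Sections 9.3.1 and 11.4.4.2 and in the laboratory manual that the central laboratory withholds all post-baseline IgE results, including those from unscheduled visits, from sites and blinded sponsor staff until the randomisation code is broken. Take IgE out of the results that the investigator must evaluate.
- **Minimum.** Bar anyone who scores EASI, IGA or SCORAD from seeing post-baseline IgE, and record the separation in the site's existing written plan of blinded and unblinded staff.
- **If the manual already masks IgE.** One confirming sentence in the protocol closes the point.
- **If values were already released.** Say so in the clinical trial report as a limitation of the blind.

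IgE collection and the planned laboratory summaries stay as they are, and no endpoint, sample size, significance level or power changes. The cost is a laboratory reporting setting and a few sentences of text. The downside is that investigators do not see one value listed under safety assessments during the trial, although no stated rule in the plan acts on it.

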5.2 Experience with investigational medicinal product

Tralokinumab is a human recombinant monoclonal antibody of the IgG4 subclass that specifically binds to human IL-13 and blocks interaction with the IL-13 receptors (13–15). A compilation of clinical and nonclinical data on tralokinumab including pharmacokinetics (PK) is given in the current version of the Investigator's Brochure.

In total, more than 4,340 subjects have been treated with tralokinumab (cut-off date: 18-Oct-2018) as determined from actual exposure data from completed clinical trials and the enrolment/randomisation schemes for ongoing trials. A phase 3 development programme is ongoing in AD, and other clinical trials with tralokinumab have been conducted in subjects with asthma, ulcerative colitis, idiopathic pulmonary fibrosis, and in healthy subjects. All

doses studied so far have had an acceptable benefit/risk profile and no major safety concerns have been identified. Possible risks associated with use of tralokinumab are summarised in Section 5.6.

In a phase 2b trial (D2213C00001), adults with moderate-to-severe AD on a background of mild to moderate topical corticosteroids (TCS) were treated with 3 different regimens of tralokinumab (45 mg every other week [Q2W], 150 mg Q2W, or 300 mg Q2W) or placebo to evaluate the safety and efficacy over a treatment period of 12 weeks. The primary endpoints were change from baseline in Eczema Area and Severity Index (EASI) at Week 12 and the percentage of subjects achieving Investigator's Global Assessment (IGA) response of 0 (clear) or 1 (almost clear) at Week 12. Secondary endpoints included change from baseline in EASI and Scoring Atopic Dermatitis (SCORAD) scores, and the percentage of subjects achieving at least 50% reduction from baseline in EASI and SCORAD scores (EASI50 and SCORAD50). In the overall intent-to-treat phase 2b population, an improvement in EASI score at Week 12 was seen in the tralokinumab 300 mg Q2W group versus placebo. 26% of subjects achieved an IGA of 0 or 1 in the tralokinumab 300 mg Q2W group versus 12% in the placebo group. The most commonly reported causally related treatment-emergent adverse event (AE) was upper respiratory tract infection (6 subjects [3.9%] in the combined tralokinumab group [45 mg, 150 mg, and 300 mg] and 2 subjects [3.9%] in the placebo group).

